5.3.2 PBR PET Scan

Image Acquisition Details:

During each visit, [11C]PBR28 (up to 15mCi, which results in ~3.7 mSv) will be injected intravenously with a slow bolus over a 30s period. The catheter will be flushed post-injection of with 0.9% saline solution. Dynamic data will be collected over approximately 90 minutes in list mode, and framed post-collection.

At the beginning of the scan session, an intravenous catheter will be placed for tracer injection. A second line will be placed in the opposite arm from the injection site and will be used to draw 2mL or 12mL blood samples throughout the test, for at most 200mL of blood. The blood draws will be used to assess the radioactivity levels in the blood necessary for dynamic imaging. The catheters will be removed at the end of the study.

Image Analysis Details:

PET volumes will be reconstructed using the ordinary Poisson ordered subsets expectation maximization (OP-OSEM) 3D algorithm. Corrections will be applied for variable detector dead time and efficiency, random coincidences, photon attenuation and scatter, and decay.

Image Interpretation Details:

Interpretation will be performed at the Martinos Center for Biomedical Imaging.

5.4 **General Concomitant Medication and Supportive Care Guidelines**

NA

5.5 **Criteria for Taking a Participant Off Protocol Therapy**

Patients may remain on study (i.e. continue with MR-PET imaging) until one of the following criteria applies:

- Intercurrent illness that prevents further participation in the imaging studies
- Unacceptable adverse event(s)

Protocol *A pilot study to evaluate PBR PET as an indicator of inflammation in brain tumor patients treated with chemoradiation or immunotherapy.*

Version Date: June 20, 2018

- Participant demonstrates an inability or unwillingness to comply with the documentation requirements or imaging studies.
- Participant decides to withdraw from the protocol (i.e. does not want to undergo further imaging studies)
- General or specific changes in the participant's condition render the participant unacceptable for further imaging studies in the judgment of the treating investigator

Participants will be removed from the protocol therapy when any of these criteria apply. The reason for removal from protocol therapy, and the date the participant was removed, must be documented in the case report form (CRF). Alternative care options will be discussed with the participant.

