13.2 Sample Size, Accrual Rate and Study Duration

Version Date: June 20, 2018

Total sample size is anticipated to be 40 patients: 15 patients in cohort A (metastatic brain tumor patients) and 15 in cohort C (GBM patients suspected of having pseudoprogression) and 10 in cohort B (GBM patients treated with immunotherapy).

Several factors influence the sample size for this study. This is a non-therapeutic study in a patient population which typically chooses to enroll in therapeutic trials if they are going to participate in a clinical trial at all so this trial will be less appealing to patients. In addition, since PBR PET remains investigational it is a very expensive test so budgetary constraints limit accrual.

In order to assess if PBR PET helps to assess tumor inflammation, we will quantitate PBR uptake in the tumor and correlate that with tumor progression as determined by the treating physician or tissue histology if obtained. The hypothesis is that if tumor PBR retention is high, this would be consistent with a strong response to immunotherapy and should be associated with prolonged progression free survival. If PBR retention is low, indicating an immunosuppressive, active tumor microenvironment, PFS should be short. We selected 9 months because by this time, we should know who has true progression since treatment related inflammation has peaked by this time.

The aim of this study is to demonstrate higher levels of PBR uptake in the non-progression group. Therefore the sample size calculation is based on two group means comparison and the test used is a one-sided two-sample equal variance t-test (with mean and SD estimates as cited below). Since there is no a priori indication for the breakdown between progression and non-progression, we assumed equal group sizes.

With 15 patients in cohort A (metastatic brain tumor patients) and 15 in cohort C (GBM patients suspected of having pseudoprogression), the study will have at least 80% power to detect a 60% difference in PBR uptake between those progression free at 9 months and those not progression free at 9 months using a one-side hypothesis test with a 0.1 significance level. By 9 months, we should know who has true progression and who has pseudoprogression. Patients who die before nine months will be considered true tumor progression. Given this conservative approach we will have the power to detect a smaller difference in PBR uptake.

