For the patients who have baseline and mid treatment PET (cohort A), we will use the change in PBR uptake. There is limited data on PBR28 in brain tumors so this calculation assumes a baseline of 125 ml/cm³ and equal variance of 100 ml/cm³ (based on literature reported rates from healthy brain).⁹ PFS at 9 months was selected as most patients would have progressed at 9 months. All patients will also be followed for 3 years after study completion for progression and survival. Time to event analysis will be used to incorporate other potential prognostic factors such as age and functional status.

Protocol *A pilot study to evaluate PBR PET as an indicator of inflammation in brain tumor patients treated with chemoradiation or immunotherapy.*

Version Date: June 20, 2018

Given the small number of patients anticipated to accrue to cohort B (GBM patients treated with immunotherapy), these patients will be analyzed with descriptive statistics alone. This accrual is anticipated to be low because of the small number of GBM patients currently treated with immunotherapy. We anticipate enrolling a maximum of 10 patients in this cohort.

Accrual Targets					
Ethnic Category	Sex/Gender				
	Females		Males		Total
Hispanic or Latino	2	+	2	=	4
Not Hispanic or Latino	3	+	8	=	11
Ethnic Category: Total of all subjects	5	+	10	=	15
Racial Category					
American Indian or Alaskan Native	0	+	0	=	0
Asian	0	+	1	=	1
Black or African American	0	+	1	=	1
Native Hawaiian or other Pacific Islander	0	+	0	=	0
White	5	+	8	=	13
Racial Category: Total of all subjects	5	+	10	=	15

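### In cohort C the t-test compares single-scan tumour uptake with no adjustment for each patient's own binding level, although binding genotype is collected; a pre-specified ANCOVA would be a cheap improvement of uncertain size

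*Combined protocol and SAP*

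**What the plan says.** The outcome in section 13.2 is tumour uptake: "we will quantitate PBR uptake in the tumor and correlate that with tumor progression as determined by the treating physician or tissue histology if obtained". It is tested with a "one-sided two-sample equal variance t-test (with mean and SD estimates as cited below"), comparing patients who are and are not progression-free at 9 months, and on the split "we assumed equal group sizes". The power claim is that "the study will have at least 80% power to detect a 60% difference in PBR uptake", "using a one-side hypothesis test with a 0.1 significance level", with 15 patients each in cohorts A and C. The planning values are given as follows: "this calculation assumes a baseline of 125 ml/cm³ and equal variance of 100 ml/cm³ (based on literature reported rates from healthy brain").

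The two tested cohorts supply different measurements. Section 13.2 uses the change in uptake for cohort A. Section 5.1 and the study calendar give cohort C one scan, at suspected pseudoprogression, so only a level is available there. Cohort B is descriptive only.

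On binding, section 2.4 says that a genetic polymorphism affects binding to the tracer and excludes low binders. Section 3.1.13 admits both high- and mixed-affinity genotypes. Section 13.3 (stratification) is marked not applicable, and 13.5 only refers back to 13.2. Age and functional status are named, but for the time-to-event analysis.

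Section 5.3.2 describes reconstruction, physical corrections and blood sampling ("The blood draws will be used to assess the radioactivity levels in the blood necessary for dynamic imaging"). It names no reference region or ratio.

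**The concern.** Write a patient's tumour value as b + g × L, where L is lesion inflammation, b an additive background and g a scaling set by that patient's binding status. A single-scan comparison, as in cohort C, carries both b and g into the t-test. With about 7 v 8 patients, a chance imbalance of mixed binders between the status groups could imitate or hide a lesion difference. Variation in b and g also adds noise.

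In cohort A the change is g × (L2 − L1): b cancels if it is stable, g does not. A separate problem arises there, because the SD of a level is used for a change.

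Accrual is limited by budget and by the study's appeal to patients (section 13.2), so precision cannot easily be bought with more patients. Section 2.4 makes further study of the tracer in phase II depend on what this pilot shows, so a null result caused by noise would matter.

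**Working it through.** **Inputs from section 13.2.** One-sided alpha 0.10; difference 0.60 × 125 = 75 ml/cm³; 1:1 split. The 100 is read as an SD: it is called a variance, but it is in ml/cm³ and the test sentence refers to SD estimates. As a true variance (SD 10), power would be about 100%.

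**Step 1: the plan's own figure.** Noncentrality = 75 / (100 × √(1/n1 + 1/n2)), with df = N − 2.
- Cohorts A and C pooled, 15 v 15: noncentrality 2.05, power 77.1% (78.0% by the normal approximation). Reaching 80% takes 17 per group.
- One cohort alone, 7 v 8: noncentrality 1.45, power 54.8%.

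The claimed 80% is nearly reached only by pooling a change score (A) with a level (C).

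**Step 2: adding a covariate.** With correlation ρ between covariate and tumour uptake, residual SD = 100 × √(1 − ρ²) and df = N − 3. The covariate is taken as balanced between status groups. No ρ is given in the documents, so the range is assumed and starts at 0.

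| ρ | Residual SD | Power, 15 v 15 | Power, 7 v 8 |
|---|---|---|---|
| 0 | 100 | 77.1% | 54.7% |
| 0.1 | 99.5 | 77.4% | 54.9% |
| 0.2 | 98.0 | 78.3% | 55.8% |
| 0.3 | 95.4 | 79.9% | 57.3% |
| 0.5 | 86.6 | 85.4% | 63.1% |
| 0.7 | 71.4 | 93.9% | 75.1% |
| 0.9 | 43.6 | >99% | 97.3% |

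Cohort C on its own is the 7 v 8 column. There, 80% power needs an SD of at most 66.0, so ρ of about 0.75 (√(1 − 0.66²)).

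**Step 3: when the covariate shares the effect.** Suppose contralateral brain carries a fraction s of the group difference, with equal SDs. The slope is then ρ and the adjusted difference is 75 × (1 − ρs).
- s = 0.5, ρ = 0.3: difference 63.75, SD 95.4, power 69.9% (15 v 15) or 48.6% (7 v 8).
- s = 0.5, ρ = 0.5: difference 56.25, SD 86.6, power 68.1% or 47.2%.
- s = 0.25, ρ = 0.3 or 0.5: 75.2% or 77.7% at 15 v 15; 53.0% or 55.2% at 7 v 8.

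These are upper bounds, because the variance inflation from a covariate that differs between groups is ignored.

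**Step 4: the SD for cohort A.** If each scan has SD 100 and the scan-to-scan correlation is r, the SD of the change is 100 × √(2(1 − r)). For r = 0, 0.25, 0.5, 0.75, 0.9 this is 141, 122, 100, 71, 45, and power at 7 v 8 is 38.6%, 44.6%, 54.8%, 75.9%, 96.8%. The planned 100 is right for a change only at r = 0.5, and r is not stated.

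**The case against.** The strongest objection is to a broader reading. A reader might infer that the whole test uses absolute uptake, that most of what it compares is background binding, and that a reference region would remove it. The documents do not support this.
- Cohort A, half of the 30 tested patients, uses change.
- The healthy-brain figure is a stand-in, used because tumour data are scarce. It does not show what tumour variation consists of; real lesions may differ mostly in inflammation. That the figure is person-to-person spread is itself an inference.
- No correlation is documented, and up to ρ = 0.2 the adjustment gains about one point or less.
- Contralateral brain is scanned after chemoradiation in cohort C and may share the inflammation. ANCOVA estimates the slope, but that does not stop it from adjusting away signal (step 3). The PET field of view is not stated, and some patients may lack a clean contralateral region.

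All of this stands, and it limits the point to cohort C and to a gain of unknown size. The objection does not reach the genotype: it is measured in every patient at screening, treatment cannot change it, and the protocol itself says that the polymorphism alters binding. Leaving it out of a single-scan comparison is not explained.

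**Conclusion.** The point holds for cohort C: one scan, both binding groups enrolled, and an unadjusted t-test. For cohort A it is narrower: proportional scaling by genotype remains, and a level's SD is applied to a change.

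On the plan's inputs, with 100 as an SD and an even split, unadjusted power is about 77% pooled and 55% within one cohort, not the claimed 80%. Adjustment could leave cohort C near 55% (ρ up to 0.2), raise it to 63–75% (ρ 0.5–0.7), or lower it to about 47–49% if contralateral brain shares half the difference (ρ 0.3–0.5). The documents cannot say which applies. This is an inexpensive improvement in method, not evidence that the planned comparison is invalid.

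**What to change.** In 13.2 and 13.5:
- For cohort C, replace the unadjusted t-test by a pre-specified ANCOVA of tumour uptake on 9-month status. Adjust for binding genotype and/or uptake in a fixed contralateral, FLAIR-normal, non-enhancing region of the same scan where one exists. Fix the choice and the region rule before any uptake is compared with outcome.
- Report the unadjusted comparison and the tumour-to-contralateral ratio as sensitivity analyses.
- For cohort A, consider genotype as a covariate for the change in uptake.
- State separate planning SDs for level (C) and change (A), and give power over correlations starting at 0, with the unadjusted figures corrected.

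The cost is plan wording, one more region on images already acquired, and one or two degrees of freedom. At ρ = 0 and 7 v 8, the first takes power from 54.8% to 54.7% and the second to 54.5% (df = N − 4). The real downside is step 3: if contralateral brain shares treatment-related inflammation, adjusting for it removes part of the signal. Genotype does not carry that risk, which favours it if only one covariate is used.

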11.1.6 Progression-Free Survival

Overall Survival: Overall Survival (OS) is defined as the time from randomization (or registration) to death due to any cause, or censored at date last known alive.

Progression-Free Survival: Progression-Free Survival (PFS) is defined as the time from randomization (or registration) to the earlier of progression or death due to any cause. Participants alive without disease progression are censored at date of last disease evaluation.

Time to Progression: Time to Progression (TTP) is defined as the time from randomization (or registration) to progression, or censored at date of last disease evaluation for those without progression reported.

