13.1 Study Design/Endpoints

This is a pilot study to test the potential utility of PBR28 PET in measuring treatment related inflammation . We will measure if increased uptake of PBR28 in the tumor during treatment is associated with longer time to progression (i.e. suggesting that the response to therapy is inflammatory rather than tumor growth).

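### Section 13.2 states at least 80% power on equal groups, yet expects most patients to have progressed by 9 months; power is 77% at an equal split and 76% to 63% if 60% to 80% have progressed

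*Combined protocol and SAP*

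**What the plan says.** Section 13.2 sets out the primary comparison: "the test used is a one-sided two-sample equal variance t-test", comparing uptake in patients progression-free at 9 months with uptake in those who are not, "using a one-side hypothesis test with a 0.1 significance level". For 15 patients in cohort A and 15 in cohort C it claims power of 80% or more to detect a 60% difference.

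On group sizes it says: "Since there is no a priori indication for the breakdown between progression and non-progression, we assumed equal group sizes". Later in the same section, in explaining the landmark, it says: "PFS at 9 months was selected as most patients would have progressed at 9 months".

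On deaths it says: "Patients who die before nine months will be considered true tumor progression". It calls this approach conservative and concludes that a smaller difference will be detectable.

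Section 13.1 frames the question differently, as whether "increased uptake of PBR28 in the tumor during treatment is associated with longer time to progression". Section 13.2 works with progression-free survival. It also mentions a further analysis: "Time to event analysis will be used to incorporate other potential prognostic factors such as age and functional status". That analysis has no stated model, time origin or place in the hierarchy. Section 13.5 refers back to the earlier text and adds nothing.

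**The concern.** The two statements about the 9-month split do not agree. One says that nothing is known about it; the other chooses the landmark because the progressed group should be the larger. For a fixed total, a two-sample t-test has most power at equal groups, so the calculation uses the most favourable split while the text expects a less favourable one.

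The remark about deaths points the wrong way or is unsupported. Classing early deaths as progression can only enlarge the progressed group. If that group is already the majority, the change moves the split further from equality and, for a given difference and SD, lowers power. The plan gives no calculation to show that the difference in uptake would become easier to detect.

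The endpoint name also varies. Under time to progression, a death without recorded progression is not an event; under PFS it is. Section 13.1 uses the first name, and section 13.2 applies the second rule.

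What is at stake is how a null result is read. In a pilot meant to decide whether the tracer merits further study, a non-significant result judged against a power of 80% or more would look more informative than it is.

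**Working it through.** **Inputs, all from section 13.2**
- Baseline uptake 125 ml/cm³; a 60% difference is 0.60 × 125 = 75.
- Spread 100 ml/cm³. The text calls it a variance, but it carries the unit of the measurement, and the section refers to mean and SD estimates. It is read here as the SD, so the standardised effect is 75/100 = 0.75. (Read as a variance, the SD would be 10 and power about 100%, which does not fit the stated figure.)
- One-sided alpha 0.10.
- N = 15 + 15 = 30, with cohorts A and C pooled. The plan does not say outright that they are pooled, but the stated power is approached only if they are. Cohort B is descriptive.
- No allowance for dropout is stated, and none is applied.

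**The plan's own figure, 15:15**

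Normal approximation: power = Φ(0.75/√(1/15 + 1/15) − 1.2816) = Φ(2.054 − 1.282) = 78.0%.

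Named t-test: noncentral t on 28 df, critical value 1.3125, noncentrality 0.75/√(1/n₁ + 1/n₂) = 2.054; power = 77.1%.

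The stated figure is reached only roughly by the normal approximation, and not by the t-test. With the t-test, 80% power at equal groups needs 17 per group, 34 in total.

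**Unequal splits, N = 30, same formula**

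| Progressed : not | √(1/n₁ + 1/n₂) | Noncentrality | Power | Difference detectable at 80% power |
|---|---|---|---|---|
| 15:15 | 0.365 | 2.054 | 77.1% | 78.7 (63% of baseline) |
| 18:12 | 0.373 | 2.012 | 75.8% | 80.3 (64%) |
| 20:10 | 0.387 | 1.936 | 73.4% | 83.5 (67%) |
| 24:6 | 0.456 | 1.643 | 63.2% | 98.4 (79%) |

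Against the t-test value at 15:15, the imbalance costs 1.3 points at 18:12, 3.7 at 20:10 and 13.9 at 24:6. The total N for 80% power is 34 at 1:1, 39 at 2:1 and 55 at 4:1.

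**Is the loss within one cohort due to the split?** For a single cohort of 15 (13 df), power is 54.8% at 8:7 and 51.8% at 10:5. Halving N takes power from 77.1% to 54.8%; the 2:1 split then costs a further 3.0 points. Low power within a cohort is mainly a matter of size.

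**Can the test fail to run?** An equal-variance t-test needs only one patient in the smaller group. If 20% are progression-free, the chance that the progression-free group is empty is 0.8¹⁵ = 3.5% in a cohort of 15 and 0.8³⁰ = 0.1% in the pooled 30.

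**The case against.** The best defence is that the plan promises little. It is a budget-limited pilot, the size of the majority is unknown, and at a moderate imbalance the loss is small: under 4 points at 2:1. The 9-month landmark also has a reason beyond event frequency. Section 13.2 expects true progression and pseudoprogression to be distinguishable by then, which matters in cohort C, where patients enter on suspected pseudoprogression and early progression dates are unreliable. All of this stands. It limits the size of the point but does not reconcile the two statements or restore 80%.

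A reader might infer more than the documents support:

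- *That only three to five patients per cohort will be progression-free.* The plan gives no number; this would require 67% to 80% progressed.
- *That the test may not be computable.* It fails only if a group is empty, which is unlikely, as shown above.
- *That event times are thrown away.* They are left out of the primary test only. The plan follows patients for 3 years and promises a time-to-event analysis, though without specifying it.
- *That the rule in section 11.1.6, under which time to progression is "or censored at date of last disease evaluation for those without progression reported", governs the analysis.* Section 11 is labelled as reference for the treating physician, and section 13.2 has its own rule for deaths.
- *That deaths necessarily skew the split beyond what the plan expects.* The sentence on the expected majority concerns PFS, which may already include them.
- *That Cox regression should replace the t-test as primary.* In illustrative simulations with N = 30, a Cox score test on continuous uptake had about 87% power against 75% for the t-test with 33% progression-free, and 76% against 61% with 20%. But those simulations assume exponential times and a log-linear effect on the hazard, which is the model that Cox fits. They include no loss to follow-up and no pseudoprogression error. In addition, cohort A's change in uptake is known only at the second scan, and a single coefficient would span a change in one cohort and a single-scan value in the other.

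**Conclusion.** The concern holds as a point about stated power and wording. Section 13.2 contradicts itself on the 9-month split, and its power claim is not met by its own inputs at any split: 77.1% at best, and about 76% to 63% if 60% to 80% of patients have progressed. These figures rest on reading 100 as the SD, on pooling cohorts A and C, and on no dropout. The range of splits is an assumption, since the plan gives no figure.

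The t-test remains valid with unequal groups; equality is an assumption of the sample-size calculation only. The remark that the handling of deaths improves sensitivity has no support in the plan. The difference between sections 13.1 and 13.2 comes down to one phrase to be aligned. The documents do not show that the primary test is invalid or that another test must replace it.

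**What to change.** 1. In section 13.2, replace the power claim with the power over a stated range of unequal splits, for example about 76% to 63% for 60% to 80% progressed. Alternatively, give the difference detectable with 80% power: about 63% of baseline at 15:15, 67% at 20:10 and 79% at 24:6. Remove the statement that the split is unknown, or reconcile it with the reason given for 9 months.
2. Delete the statement that counting deaths as progression gives power for a smaller difference.
3. In section 13.1, change time to progression to PFS, to match section 13.2.
4. Optionally, specify the planned time-to-event analysis as a key supportive analysis of continuous uptake. Measure time from the scan that supplies the uptake value (the second scan in cohort A), standardise uptake within cohort, and stratify the model by cohort. Any gain in power should be described as illustrative.

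Items 1 to 3 cost only wording; no patients, scans or follow-up are added. Item 4 uses data already to be collected; its downside is reliance on proportional hazards in a small sample.

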1.2 Primary Objectives

1. To determine whether PET imaging with [11C] PBR28 can measure inflammation related to immunotherapy in patients with brain tumors- specifically metastatic brain tumors and glioblastoma. .
2. To determine whether PET imaging with [11C] PBR28 can measure inflammation related to chemoradiation in patients with glioblastoma.

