One goal with including both glioma patients and metastatic brain tumor patients is to determine if there are differences in PBR28 uptake based on type of cancer which may suggest differences in TSPO expression within different tumor microenvironments and in inflammatory response to treatment. Given the limited data on this tracer in cancer, it may be more useful in one type of cancer rather than another because of the different underlying biology of tumors. There is a high number of patients with metastatic melanoma to the brain and immunotherapy is commonly used for this patient population so we elected to start with this cohort of patients but are now amending the protocol to include all cancer types as there are now immunotherapy options and clinical trials of immunotherapy for more than just melanoma patients.

Thus, we will evaluate [11C]PB28 PET as a tool for measuring inflammation associated with the response to immunotherapy or chemoradiation in patients with brain tumors. Having such a tool that distinguishes active tumor from inflammation will be an incredibly useful tool in the management of patients. If this tracer shows potential utility in this pilot study, we will examine

Version Date: June 20, 2018

it further in separate planned phase II glioma vaccination studies at our center, in an effort to correlate PET findings with outcome.

One limitation of PBR PET is that certain people can be classified as low binders because of a genetic polymorphism.¹⁴ These “low binders” have negligible binding to the PBR28 tracer so would not be informative to include in our study and will be excluded. Only about 10% of human subjects are low affinity binders based on prior data.¹⁴ As part of the screening process, after informed consent has been obtained, a simple blood test will be performed to determine binding affinity of consented patients. Those who are low-affinity binders will be not be enrolled.

In summary, we our simple goal is to perform two PBR PETs in patients with metastatic brain cancer undergoing treatment with immunotherapy and one PBR PET in patients with GBM to measure inflammation. This is similar to performing FDG PETs in these patients but uses a different PET tracer than FDG. Since PBR28 was first used at the Martinos Center, there have been 11 clinical trials approved using this tracer and no adverse events reported.

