5. IMAGING PLAN

5.1 Treatment Regimen

This study does not add any additional treatment to enrolled patients. All treatment decisions will be at the discretion of the treating physician. There will be no change in the diagnosis or management of the patient based on any procedures or tests carried out as a part of this study.

There are no expected toxicities and potential risks for PBR. All scans will be performed at the Martinos Center for Biomedical Imaging in Charlestown on the combined MR PET scanner.

For GBM patients with suspected pseudoprogression, MR-PET will be performed at the time of suspected pseudoprogression.

For GBM patients treated with immunotherapy, MR-PET will be performed prior to start of the immunotherapy and then 2 cycles later.

For metastatic cancer patients treated with immunotherapy, MR-PET will be performed prior to start of the immunotherapy and then 3 cycles later.

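### One power statement pools cohort A (change between two scans) with cohort C (one scan); neither primary objective has its own test, and each cohort alone has about 55% power, not 80%

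*Combined protocol and SAP*

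**What the plan says.** Section 1.2 has two primary objectives. The first is whether the tracer can measure "inflammation related to immunotherapy in patients with brain tumors- specifically metastatic brain tumors and glioblastoma"; the second asks the same about chemoradiation in glioblastoma. Under Section 3.1, cohorts A (metastases) and B (GBM) receive immunotherapy, and cohort C is GBM with suspected pseudoprogression after chemoradiation.

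Section 5.1 gives cohort C one scan. Cohort A is scanned before immunotherapy and again 3 cycles later. For cohort B: "For GBM patients treated with immunotherapy, MR-PET will be performed prior to start of the immunotherapy and then 2 cycles later". The study calendar agrees, placing the second scan before cycle 4 in A and before cycle 3 in B.

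Section 13.2 compares uptake between patients who are and are not progression-free at 9 months: "the test used is a one-sided two-sample equal variance t-test". For 15 patients in A and 15 in C, "the study will have at least 80% power to detect a 60% difference in PBR uptake", "using a one-side hypothesis test with a 0.1 significance level". The inputs are given once: "this calculation assumes a baseline of 125 ml/cm³ and equal variance of 100 ml/cm³". Change in uptake is assigned to the patients with two scans, identified in parentheses as cohort A only. Because few are expected in cohort B (at most 10), "these patients will be analyzed with descriptive statistics alone". A time-to-event analysis with prognostic factors is mentioned, but not tied to a cohort or an objective. Section 13.5 only refers back.

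**The concern.** There are two primary objectives but one power statement, and that statement cuts across them. Cohort A supplies a change between two scans under immunotherapy; cohort C supplies one uptake value after chemoradiation. These are different quantities answering different questions. A two-sample t-test on the 30 values together would not say whether the tracer works in either setting, and the plan does not say how the two measures would be put on one scale.

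The GBM half of Objective 1 rests on cohort B, which enters no test. The parenthesis that equates two-scan patients with cohort A also leaves B without a stated outcome measure, although Section 5.1 and the calendar give B two scans. The summary at the end of Section 2.4 speaks of a single scan in GBM patients, which conflicts with both.

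At stake is what the pilot can claim. If each objective is analysed in its own cohort, readers will take 80% as the power of each analysis when it is far lower.

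**Working it through.** **Inputs (Section 13.2).** Difference = 60% of 125 = 75 ml/cm³. The figure of 100 is called a variance but carries the units of uptake, and the same section refers to mean and SD estimates, so it is read as the SD. (As a variance the SD would be 10 and power about 100% at every size here.) One-sided alpha 0.10, equal split, no dropout.

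**Formula.** SE = SD × √(1/n₁ + 1/n₂); noncentrality = 75/SE; power from the noncentral t with n₁ + n₂ − 2 df.

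**The plan's own figure.** A and C pooled, 15 v 15: SE = 100 × √(2/15) = 36.5; noncentrality 2.05; critical value 1.313 (28 df); power **77.1%**. The normal approximation gives 78.0%. Among analyses of A and C, only pooling comes near 80%; even so, the normal approximation needs 17 per group to reach it.

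**One cohort of 15.** A or C alone, 7 v 8: SE = 100 × √(1/7 + 1/8) = 51.8; noncentrality 1.45; critical value 1.350 (13 df); power **54.8%**. Difference detectable with 80% power: about 114 ml/cm³, and 114/125 = 91%. With 30 pooled it is about 79 ml/cm³ (63%).

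**Cohort B alone.** 5 v 5: SE 63.2; power 43.7%; 90% CI half-width 1.860 × 63.2 = 118 ml/cm³ (A alone: 92).

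**Supportive A+B analysis of change with a cohort term.** Each cohort contributes information 1/(1/n₁ + 1/n₂): A 3.73, B 2.50, total 6.23. SE = 100/√6.23 = 40.1 with 25 − 3 = 22 df, and the 90% CI half-width is 69 ml/cm³. If the effect in B is a fraction r of that in A, the expected estimate is 75 × (3.73 + 2.50r)/6.23.

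| Scenario | Power, A+B | Power, A alone |
|---|---|---|
| 10 in B, r = 1 | 71% | 55% |
| 5 in B (2 v 3), r = 1 | 63% | 55% |
| 10 in B, r = 0.5 | 57% | 55% |
| 10 in B, r = 0.4 | 55% | 55% |
| 10 in B, r = 0 | 43% | 55% |
| 20% progression-free (A 3 v 12, B 2 v 8), r = 1 | 58% | 44% |
| 20% progression-free, r = 0.5 | 46% | 44% |

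Break-even is at r of about 0.4. The 20% row is an assumption; it is included because Section 13.2 expects most patients to have progressed by 9 months, which sits badly with an equal split.

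**SD of change.** None is given. If both scans have SD 100 and correlation ρ, the SD of change is 100 × √(2(1 − ρ)), which equals 100 only at ρ = 0.5. At SD 80 (ρ = 0.68), power is 68% for A alone and 84% for A+B; at SD 140 (ρ = 0.02), 39% and 51%.

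**The case against.** This is a pilot limited by budget and accrual, and Section 13.2 says openly why cohort B is kept descriptive. That stands: it is a disclosed choice, not an oversight. But it does not explain why Objective 1 names glioblastoma as if it would be assessed like metastases, and smallness applies to A alone nearly as much (55% power against 44% for B).

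A reader might infer that Objective 1 is tested on 15 patients when 25 were available. The documents do not support that. No 15-patient test is written; the only power figure is approached with A and C pooled to 30. The 55% is what follows if the analysis is done by cohort, which is an inference.

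A reader might also conclude that A+B should be the primary test of Objective 1. That goes too far. The second scan follows 3 cycles in A and 2 in B; Section 3.1 requires monotherapy in A but not in B; Section 11.1 recommends RECIST for metastases and RANO otherwise; and Section 2.4 makes differences between tumour types a goal of the study. A cohort term absorbs a shift in average change, not a different effect, and at half the effect in B the gain is about 3 points.

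Nor is cohort B thrown away. Section 2.4 makes the "separate planned phase II glioma vaccination studies at our center" depend on the tracer showing potential utility, not on a significance test, and B's descriptive results remain available for that judgement.

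Finally, separating the objectives replaces one test at 77% with two weaker ones. That is true, but the pooled test mixes a change with a single value, so its higher power is for a question that neither objective asks.

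**Conclusion.** The point holds in this form: Sections 13.2 and 13.5 define no separate test for either primary objective, the single power statement combines two different quantities, and the GBM part of Objective 1 has no inferential analysis. The claimed 80% is 77% by the named t-test when A and C are pooled, and about 55% for either cohort alone.

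These figures assume that 100 is the SD, that it applies to change as well as to single-scan uptake, an equal outcome split and no dropout. A less even split or a larger SD of change lowers them; a smaller SD raises them. The case for adding B is conditional: a useful gain if the effect is similar in both tumour types and B accrues well, little at half the effect, and a loss below about 40% of A's effect. That supports a secondary, cohort-stratified analysis and no more.

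**What to change.** - **Sections 13.2 and 13.5:** state the analysis of Objective 1 (change in uptake, with cohort A carrying the test) and of Objective 2 (single-scan uptake, cohort C) separately. Restate the power of each as about 55% for a 75 ml/cm³ difference, or give the detectable difference of about 114 ml/cm³. Call the 100 an SD, and state the SD assumed for change.
- **Number of scans in GBM:** reconcile the summary in Section 2.4 with Section 5.1 and the calendar. On the two-scan schedule in those sections, the parenthesis in 13.2 should extend the change measure to cohort B.
- **Cohort B:** report its own estimate with a confidence interval, and say in Objective 1 that its GBM part is exploratory.
- **Supportive analysis:** prespecify a linear model of change in A and B with cohort as a stratum, shown beside the cohort-specific estimates and not in place of them.

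The cost is wording only, with no added patients or scans. There are three downsides. The stated power looks less favourable. Two one-sided 0.10 tests replace one, so if they are independent the chance of at least one false positive is 1 − 0.9² = 19%. The A+B estimate averages over different scan timing, monotherapy rules and tumour types.
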